### 3 STUDY OBJECTIVE

The primary objective of this study is to evaluate, for the visual correction of aphakia and presbyopia, the safety and effectiveness of the RxSight Light Adjustable Lens (LAL) to provide an extended depth of focus (improve intermediate and near visual acuity without compromising distance visual acuity) in subjects who have undergone bilateral implantation with the LAL and subsequent light treatments for refractive and presbyopia correction (LAL group). To assess for effectiveness, a control group consisting of subjects bilaterally implanted with commercially available IOLs (SofPort LI61AO monofocal IOL, Bausch + Lomb) (Control group) will be used. Primary effectiveness will be demonstrated by comparing monocular measurements of depth of focus (DOF), photopic distance corrected intermediate visual acuity (67 cm), and photopic best corrected distance visual acuity (4 meters) between primary eyes in the LAL group and Control group at the Postop Month 6 visit. Secondary effectiveness will be demonstrated by comparing monocular measurements of primary eyes of photopic uncorrected distance visual acuity (UCDVA) (4 meters)/uncorrected intermediate visual acuity (UCIVA) (67 cm)/uncorrected near visual acuity (UCNVA) (40 cm) and monocular measurements of primary eyes of photopic uncorrected distance visual acuity (4 meters) and photopic distance corrected near visual acuity (40 cm) between the LAL group and Control group at the Postop Month 6 visit.

### 4 STUDY DESIGN

A prospective, randomized, controlled, multi-center, clinical study will be conducted at a maximum of 11 sites located in the United States. Subjects will be followed for a 6 month period. A minimum of 20 subjects will undergo study implantation at each participating site, with less than 25% of the total study population implanted at one clinical site.

Patients who require bilateral cataract extraction and intraocular lens implantation and who wish to improve their depth of focus will be pre-screened for eligibility as part of pre-entry activity. If it is determined that the patient may be eligible to participate, delegated and trained study staff will explain the study purpose, procedures, risks/benefits and subject responsibilities to the potential participant. Written informed consent must be obtained prior to initiation of any clinical procedures that are performed solely for the purpose of determining eligibility for. The patient is enrolled upon signing the informed consent. Both eyes of all subjects must be screened for eligibility at the same preoperative visit. If at any time during the preoperative screening, either eye does not meet inclusion or exclusion criteria, screening for that subject should be discontinued and the subject will be exited from the study. Subjects that meet all inclusion/exclusion criteria will be randomly assigned in a 1:1 ratio to either the LAL group or Control group. In addition, each eye of the subject will be assigned as either the primary eye or fellow eye. Pre-determined randomization schemes will be utilized. The primary eye of each subject will be scheduled for surgery first with implantation of the fellow eye separated by 7 to 14 days.

All study eyes will be targeted for post cataract surgery emmetropia as measured on a 4 meter exam lane. If surgical complications (either prior to attempting to implant the study IOL or after study IOL implantation has been attempted) occur with the primary eye and no IOL is implanted,

the subject should be followed until any adverse event that may have occurred is stable or has resolved per the investigator's assessment; at which time the subject should be exited from the study. No study IOL should be implanted in the fellow eye. Subjects that have successful implantation of a study IOL in the primary eye but not the fellow eye will not be required to have monocular clinical measurements of their fellow eye performed throughout the study.

Subjects randomized to the LAL group

Commencing at the Postop Week 3 [REDACTED] visit (17-24 days post-Fellow eye operative visit), both eyes will receive an [REDACTED]  
[REDACTED]

At the Adjustment #1 visit (3-7 days after the Postop Week 3 [REDACTED] visit), both eyes will receive an adjustment #1 light treatment based on the measured manifest refraction at 4 meters at this visit. Eyes measured with a manifest cylinder of  $\geq 0.50$  D will receive a spherocylindrical light treatment while eyes with  $< 0.50$  D of manifest cylinder will receive a non-astigmatic light treatment.

At the Adjustment #2 visit (3-7 days after the Adjustment #1 visit), both eyes will receive an adjustment #2 light treatment also based on the measured manifest refraction at 4 meters at this visit. Eyes measured with a manifest cylinder of  $\geq 0.50$  D will receive a spherocylindrical light treatment while eyes with  $< 0.50$  D of manifest cylinder will receive a non-astigmatic light treatment.

[figure not shown]
Three to 7 days after the Adjustment #2 light treatment, both eyes will be eligible to receive an adjustment #3 light treatment. If the eye's |MRSE| is  $\geq 0.25$  D OR manifest cylinder is measured at  $\geq 0.50$  D, then the eye will receive an adjustment #3 light treatment; otherwise the eye will be eligible to proceed to lock-in #1.

The lock-in #1 light treatment will be performed in the primary eye 3 to 7 days after the subject's final adjustment light treatment followed 3 to 7 days later by the lock-in #2 treatment, if needed. The lock-in #1 treatment will be performed in the fellow eye 3 to 7 days after the final lock-in in the primary eye and after confirmation that there has been no ultraviolet (UV) retinal damage per Sections 7.3.2.1 and 7.3.2.2 followed 3 to 7 days later by lock-in #2, if needed. Subjects in the LAL group will receive [REDACTED], up to three spherocylindrical/non-astigmatic light treatments, and one or two lock-in treatments in each eye.

Examinations will occur at regular intervals over a 6 month period to evaluate the safety and effectiveness outcomes. For eyes in the LAL group, if an eye is diagnosed with ultraviolet (UV) retinal damage, an additional follow-up exam will be added at 12 months postoperatively to confirm resolution or document sequelae, if any. Masked examiners will be utilized at the Postop Month 6 visit.

Safety for all study eyes will be evaluated per ISO 11979-7.

The following flowchart illustrates the enrollment and the adjustment process for the proposed study.

## DURATION OF STUDY

Each subject will participate in the study for approximately 6 months. The recruitment phase is expected to last approximately 14 months. The complete study period is expected to be approximately 20 months.

## STUDY SITE

The study will be performed in ophthalmology clinics. The investigators will be ophthalmic surgeons trained in cataract surgery with implantation of intraocular lenses. Study responsibilities will be registered in a delegation log that will be kept at the investigational site. The overall responsibility at the study clinic remains with the investigator.

## 5 OUTCOME PARAMETERS

### 5.1 EFFECTIVENESS PARAMETERS

#### *Primary Endpoints*

- Monocular Depth of Focus (DOF) measured at the logMAR 0.20 level at Postop Month 6

At Postop Month 6, the LAL group (primary eyes) demonstrates at least 0.5 D greater monocular photopic negative lens induced distance-corrected depth of focus compared to the Control group (primary eyes) at 0.20 logMAR visual acuity threshold.

- Monocular Distance Corrected Intermediate Visual Acuity (DCIVA) at 67 cm at Postop Month 6

At Postop Month 6, the LAL group (primary eyes) demonstrates statistical superiority over the Control group (primary eyes) on mean photopic monocular distance corrected intermediate visual acuity (DCIVA) at 67 cm. [one-sided test using level of significance of 0.025].

- Outcome of Monocular DCIVA at 67 cm better than or equal to 0.20 logMAR for the LAL group at Postop Month 6

At Postop Month 6, the proportion of the LAL primary eyes reaching this outcome is at least 50%. In other words, the median of photopic monocular DCIVA at 67 cm for the LAL group (primary eyes) is at least 0.20 logMAR.

- Monocular Best Corrected Distance Visual Acuity (BCDVA) at Postop Month 6

At Postop Month 6, the LAL group (primary eye) is statistically non-inferior to the Control group (primary eyes) on mean, monocular photopic BCDVA using a non-inferiority margin of 0.10 logMAR.

[REDACTED]

*Secondary Endpoints*

The secondary effectiveness endpoints listed below will be [REDACTED]

[REDACTED]

- Monocular photopic Distance Corrected Near Visual Acuity (DCNVA) at 40 cm at Postop Month 6

At Postop Month 6, the LAL group (primary eyes) demonstrates statistical superiority over the Control group (primary eyes) on mean photopic monocular DCNVA at 40 cm [one-sided test using level of significance of 0.025]

- Outcome of Monocular photopic DCNVA at 40 cm better than or equal to 0.20 logMAR at Postop Month 6

At Postop Month 6, the proportion of the LAL primary eyes reaching this outcome is at least 50%. In other words the median of monocular photopic DCNVA at 40 cm for the LAL group (primary eyes) is at least 0.20 logMAR.

- [REDACTED]

- Monocular photopic Uncorrected Distance Visual Acuity (UCDVA) using a +0.25 D lens at Postop Month 6

At Postop Month 6, the LAL group (primary eyes) demonstrates statistical superiority over the Control group (primary eyes) on mean monocular photopic UCDVA using a +0.25 D lens [REDACTED]

The analyses of the secondary effectiveness endpoints [REDACTED]

## 5.2 SAFETY PARAMETERS

### *Primary Endpoint*

- Incidence of ocular serious adverse events including persistent and cumulative events defined per ISO 11979-7

The ISO-event rates for all subjects in the LAL group and Control group will be presented separately. Additionally, the event rate of the LAL subjects will be compared to the “safety and performance endpoints (SPE)” rates specified in ISO.

[REDACTED]

[REDACTED]

[REDACTED]

[REDACTED]

[REDACTED]

The incidence of all other adverse events will also be presented separately for the LAL group and Control group. In addition, the incidence of secondary surgical intervention (SSI) related to the optical properties of the lens will be provided.

## 6 STUDY POPULATION

The study population will consist of up to 350 subjects enrolled (informed consent form signed) to allow for up to 230 subjects with implantation of either the LAL IOL or Control IOL attempted in the Full Analysis Set (FAS). An additional 17 subjects were implanted in the pre-COVID-19 population. Each subject will desire to improve their depth of focus (improve intermediate and near visual acuity without compromising distance visual acuity), will be good candidates for bilateral IOL implantation, and will agree to participate in a randomized clinical study. Study subjects will be randomized 1:1 to either undergo bilateral LAL implantation and light treatments for refractive and presbyopia correction (LAL group) or to undergo bilateral implantation with commercially available IOLs (SofPort LI61AO monofocal IOL, Bausch + Lomb) (Control group). All study subjects must have preoperative keratometric astigmatism of <0.75 D in both eyes. Subject's eyes must meet all other applicable inclusion criteria and none of the exclusion criteria.

### 6.1 INCLUSION CRITERIA

- Must sign a written Informed Consent Document and be willing to undergo cataract surgery for bilateral implantation of either the LAL or SofPort LI61AO IOL (Bausch + Lomb).
- Must be willing to be randomized to either the LAL group (bilaterally implanted with the LAL and receive light treatments for refractive and presbyopia correction) or the Control group (bilateral implantation with the SofPort LI61AO monofocal IOL).
- Between the ages of 40 and 80 inclusive on the day the first cataract surgery is performed.
- Preoperative keratometric cylinder <0.75 D in both eyes.
- Cataractous lens changes as demonstrated by best corrected distance visual acuity (BCDVA) of 20/40 or worse with or without a glare source in both eyes.
- Best corrected distance visual acuity projected to be 20/20 or better after cataract removal and intraocular lens (IOL) implantation in both eyes as estimated by potential acuity meter (PAM) or surgeon estimation.
- Clear intraocular media other than cataract in both eyes.
- Willing and able to comply with the requirements for study specific procedures and visits.
- [REDACTED] .
- Able to complete a written questionnaire in English.
- Requires an IOL power within the range available for both the LAL and SofPort LI61AO IOLs.

## 6.2 EXCLUSION CRITERIA

- Pseudoexfoliation in either eye.
- Pre-existing macular disease in either eye.
- Patient with sufficiently dense cataract that precludes examination of the macula in either eye.
- Retinal degenerative disorder that is expected to cause future vision loss in either eye.
- Diabetes with any evidence of retinopathy in either eye.
- Evidence of glaucomatous optic neuropathy in either eye.
- History of uveitis in either eye.
- Significant anterior segment pathology, such as rubeosis iridis, aniridia, or iris coloboma in either eye.
- Pupil that is deformed including ectopic pupil condition in either eye.
- Corneal pathology that is either progressive or sufficient to reduce BCDVA to worse than 20/20 in either eye.
- Any corneal dystrophy including basement membrane dystrophy in either eye that in the opinion of the investigator may confound the outcome.
- Keratoconus or suspected of having keratoconus in either eye.
- Has undergone previous corneal or intraocular surgery in either eye, except eyes with previous pterygium excision are permitted as long as the pterygium did not extend more than 2mm onto the cornea from the limbus.
- Subjects with serious co-morbid conditions that in the judgment of the investigator makes inclusion in the study not in the best interest of the subject.
- Subjects taking systemic medication that may increase sensitivity to UV light such as tetracycline, doxycycline, psoralens, amiodarone, phenothiazines, chloroquine, hydrochlorothiazide, hypericin, ketoprofen, piroxicam, lomefloxacin, and methoxsalen. LDD treatment in patients taking such medications may lead to irreversible phototoxic damage to the eye. This is only a partial list of photosensitizing medications. Please evaluate all medications that the patient is taking for this effect prior to consideration for implantation.
- Subjects taking a systemic medication that is considered toxic to the retina such as tamoxifen.
- Subjects who the doctor believes will be unable to maintain steady fixation that is necessary for centration of the LDD light treatment in either eye.
- Irregular astigmatism in either eye.
- History of ocular herpes simplex virus in either eye.

- Previous trauma or developmental defects in which appropriate support of the intraocular lens (IOL) is not possible in either eye.
- Current vitreoretinal disease or a high risk for future vitreoretinal disease that may require silicone oil as part of therapy in either eye.
- [REDACTED]
- Subject who has participated within another ophthalmic clinical trial within the last 3 months.

[figure not shown]

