## 7.2 SUBJECT ENTRY

If a COVID-related public health emergency declaration is in place at the time of the study, the study site should take appropriate measures in a clinic setting to minimize spread of the virus in conformance to professional society guidelines and applicable guidance from the states and counties in which the sites are located.

Patients who require bilateral cataract extraction and intraocular lens implantation and who wish to improve their depth of focus will be pre-screened for eligibility as part of pre-entry activity. If it is determined that the patient may be eligible to participate, delegated and trained study staff will explain the study purpose, procedures, risks/benefits and subject responsibilities to the potential participant. Procedures that are performed as part of a routine cataract evaluation and which (1) would be done whether or not study entry was contemplated (2) are done in accordance with the protocol-specific clinical methods (3) are completed within the protocol Preop window and (4) are done by trained team members on the delegation log may be performed and the results subsequently used for determining study eligibility without first obtaining consent.

Written informed consent must be obtained prior to initiation of any clinical procedures that are performed solely for the purpose of determining eligibility for research. The subject will sign and date the informed consent form in the presence of the person conducting the consent process. The investigator and/or the person conducting the consent process will also sign and date the consent form. The patient is enrolled upon signing the informed consent and a study ID is assigned.

The preoperative examination will be performed no more than 60 days prior to surgery for either the Primary eye or the Fellow eye. Both eyes of all subjects must be screened for eligibility at the same preoperative visit. If the 60-day time period elapses, it is acceptable for patients to be re-screened by undergoing a complete preoperative examination. If at any time during the preoperative screening, either eye does not meet inclusion or exclusion criteria, screening for that subject should be discontinued and the subject will be exited from the study. All study subjects must have preoperative keratometric astigmatism of <0.75 D in both eyes. Subject's eyes must meet all other applicable inclusion criteria and none of the exclusion criteria.

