The principal investigator or delegated MD Sub-Investigator will review the Inclusion/Exclusion checklist document provided for the study and, if the subject is eligible, sign and date the form. The documentation of eligibility must be completed prior to implantation. Subjects that meet all inclusion/exclusion criteria will be randomly assigned in a 1:1 ratio to either the LAL group or the Control group. In addition, each eye of the subject will be assigned as either the primary eye or the fellow eye based on randomization. Pre-determined randomization schemes will be utilized. A randomization schedule for the treatment assignments (LAL versus Control) with a block of 4 and a ratio of 1:1 will be generated using a random generator such as SAS. Randomization of subjects will occur immediately prior to commencing cataract surgery on the primary eye. Only subjects meeting all inclusion/exclusion criteria may be implanted. Those subjects who do not meet the inclusion/exclusion requirements will be considered screen failures. Exit forms will be completed for all screen fails. Up to 350 subjects may be enrolled to allow for up to 230 subjects who will have had implantation of the LAL IOL or Control IOL attempted in the FAS. An additional 17 subjects were implanted in the pre-COVID-19 population.

The implant lens powers for the LAL and Control IOLs will be calculated based upon ocular biometry data and a lens power formula of the investigator's choice. Optimized lens constants of the investigator's choice also may be utilized. These lens constants will not be changed during the clinical investigation. For all study eyes, a postoperative spherical equivalent (SE) outcome closest to emmetropia as measured on a 4 meter exam lane will be targeted. The lens power will not be altered based on intraoperative diagnostics.

Subjects randomized to the LAL group

Commencing at the Postop Week 3 [REDACTED] visit (17-24 days post-Fellow eye operative visit), both eyes will receive an [REDACTED]  
[REDACTED]

At the Adjustment #1 visit (3-7 days after the Postop Week 3 [REDACTED] visit), both eyes will receive an adjustment #1 light treatment based on the measured manifest refraction at 4 meters at this visit. Eyes measured with a manifest cylinder of  $\geq 0.50$  D will receive a spherocylindrical light treatment while eyes with  $< 0.50$  D of manifest cylinder will receive a non-astigmatic light treatment.

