### 7.3.2.1 Postponement of Light Treatment Procedure(s)

LDL treatments should be delayed in both eyes if any of the following new symptoms or changes in performance are noted in either study eye;

- Color Vision Testing: Treatment should be delayed if the subject scores worse on Part 2 of the City University Color Test than the Postop Week 3 visit for Tritan evaluation.
- Erythropsia Evaluation: With any score of 2 (red), the treatment should be delayed.
- Best Corrected Distance Visual Acuity: With any loss of BCDVA (unless the cause is known to be non-retinal) of 10 letters or more on an ETDRS (logMAR) chart compared to the Postop Week 3 visit BCDVA, treatment should be delayed.

The subject should return for follow-up visits until the subject's visual assessment of erythropsia is a score of 0 or 1 (indicates the paper looks white or pink), the BCDVA is within 10 letters of the Postop Week 3 visit BCDVA and an equivalent or better score than the Postop Week 3 visit test is measured in the Tritan section of the City University Color Test, at which time the next LDL treatment may be delivered.

- If sutures were utilized at the time of surgery to close the incision wound, light treatments should not commence on the eye until a minimum of 4 weeks after suture removal.
- An eye with an ocular adverse event that could be negatively impacted by light treatment or negatively impact the effectiveness or safety of a light treatment should have light treatments delayed until after the adverse event has subsided. This includes corneal edema and superficial punctate keratitis (SPK) (Grade 3 (moderate) or more severe), retinal conditions including diabetic retinopathy and cystoid macular edema, epithelial defect, endophthalmitis

or any other safety concern that the investigator believes may be negatively impacted by light treatment.

- If an eye is discovered with evidence of premature photopolymerization as evidenced as a zone on the lens surface, the investigator should contact the Sponsor for further instructions. (see Appendix 1 for additional details regarding premature photopolymerization).

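### A photosensitizing drug started after entry is not a listed reason to hold UV light treatment, although Section 6.2 names that treatment as the hazard

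*Combined protocol and SAP*

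**What the plan says.** Section 6.2 (repeated in 1.5) excludes subjects taking systemic drugs that raise UV sensitivity, gives a list it calls partial, and warns that "LDD treatment in patients taking such medications may lead to irreversible phototoxic damage to the eye". A separate criterion excludes drugs toxic to the retina, such as tamoxifen. On timing, 6.2 instructs: "Please evaluate all medications that the patient is taking for this effect prior to consideration for implantation".

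Section 7.2 places randomization at surgery ("Randomization of subjects will occur immediately prior to commencing cataract surgery on the primary eye") and adds that "Only subjects meeting all inclusion/exclusion criteria may be implanted". On the screening window it says: "The preoperative examination will be performed no more than 60 days prior to surgery for either the Primary eye or the Fellow eye".

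Section 7.3.2.1 governs when UV is postponed. Its first group of triggers is introduced by the statement that "treatments should be delayed in both eyes if any of the following new symptoms or changes in performance are noted in either study eye": a worse Tritan score, an erythropsia score of 2, or a BCDVA loss of 10 letters or more. It then lists sutures, ocular adverse events, premature photopolymerization and capsular haze. An eye with a relevant ocular adverse event "should have light treatments delayed until after the adverse event has subsided". That same bullet ends with "any other safety concern that the investigator believes may be negatively impacted by light treatment".

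**The concern.** The hazard in 6.2 is UV delivery while a subject is on the drug. The readable control acts at entry, and UV delivery starts weeks afterwards and runs over several sessions. A subject who begins, say, doxycycline (named in 6.2) between surgery and lock-in would have been ineligible at entry for a reason that now applies directly. Yet a site working through the 7.3.2.1 list is not told to stop or to call anyone. Holding treatment depends on the investigator connecting the 6.2 warning to a general phrase at the end of a bullet on another subject.

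The adverse-event route may not bring the drug to light. Section 9.6 requires documentation of ocular AEs, ocular SAEs and systemic SAEs, so a non-serious systemic illness treated with a listed drug need not be recorded as an AE.

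At stake is eye damage that 6.2 says may be irreversible.

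**Working it through.** **1. The rules side by side.**

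| Section | What it controls | Does it name a drug started after entry? |
|---|---|---|
| 6.2 | Entry; review tied to implantation | No |
| 7.3.2.1 | Reasons to delay UV (no redaction marks) | No; investigator-judgment catch-all only |
| 7.3.2.2 | OCT and further testing after a change is seen | No (readable text) |
| 7.3.2.3 | Preparation, dilation, required measurements first | No (readable text) |
| 7.3.2.4, 7.3.2.5 | Adjustment and lock-in steps | No (readable text) |

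The catch-all permits a delay. But its bullet ends the delay when an adverse event subsides, and a drug exposure is not an event of that kind.

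**2. Treatment days.** The inputs are the windows in Section 7.5, counted from fellow-eye surgery.

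| Visit | Earliest | Latest |
|---|---|---|
| Week 3 treatment (first UV) | 17 | 24 |
| Adjustment #1 | 17+3 = 20 | 24+7 = 31 |
| Adjustment #2 | 23 | 38 |
| Adjustment #3 | not needed | 45 |
| Primary-eye lock-in #1 | 26 | 52 |
| Primary-eye lock-in #2 | not needed | 59 |
| Fellow-eye lock-in #1 | 29 | 66 |
| Fellow-eye lock-in #2 | not needed | 73 |

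So the last UV session falls between Day 17 + 4×3 = 29 and Day 24 + 7×7 = 73.

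**3. Age of the medication review.** Primary-eye surgery is 7 to 14 days before fellow-eye surgery.

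- Review reconfirmed on the day of primary-eye surgery:
  - first UV: 7+17 = 24 to 14+24 = 38 days;
  - last primary-eye lock-in: 7+26 = 33 to 14+59 = 73 days;
  - last fellow-eye lock-in: 7+29 = 36 to 14+73 = 87 days.
- Review not repeated after a preoperative exam 60 days before fellow-eye surgery (upper limit): first UV 60+24 = 84 days; last lock-in 60+73 = 133 days.

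**4. UV sessions per eye.** The fewest are 1 (Week 3) + 2 adjustments + 1 lock-in = 4. The most are 1 + 3 + 2 = 6. The Week 3 treatment is partly redacted and is assumed to be one session.

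**5. Room for a hold.** From the last lock-in to the close of the Month 3 window (Day 90): 90−73 = 17 to 90−29 = 61 days. To the close of the Month 6 window (Day 180): 180−73 = 107 to 180−29 = 151 days.

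**The case against.** The strongest reply is that the deciding evidence cannot be read. History of Medications is item 6 of the assessments in 7.6, but the readable part of Table 1 starts at item 15. A Table 1 footnote about unscheduled visits before the final lock-in has no surviving row. If medications are reviewed at the light-treatment visits, 7.3.2.3 would require that review before UV is given. The LDD Operator's manual, which 8.3.4 treats as binding, the LDD input screens, Appendix 1, the source document templates and the consent form could also contain a check. This limit stands, and it is why the claim is that the readable rules do not list the drug, not that the whole plan lacks a check. It does not close the gap: recording a drug is not an instruction to withhold UV, and no readable rule links the two.

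Second, the 6.2 warning together with the catch-all gives the investigator authority to hold. That is true, but it remains discretionary. For lesser hazards 7.3.2 sets specific preventive holds: 4 weeks after suture removal and 48 hours after YAG.

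Third, each site's perioperative regimen is approved by the medical monitor (7.3, 7.4). This narrows the exposure but does not reach drugs prescribed elsewhere.

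Fourth, other protections exist: the lens has a UV-filtering posterior layer (7.1.1), both eyes are delayed on a change in either, and fellow-eye lock-in waits until the primary eye shows no UV damage. These limit exposure or further harm. None stops a first exposure on the drug, and the adjustments are bilateral.

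Fifth, the day counts describe the age of a review, not a risk, and depend on when the review last took place. If it were repeated at fellow-eye surgery, it would be 17 to 24 days old at first UV and 29 to 73 days old at the last lock-in. This is fair, and the number of subjects at risk cannot be given.

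**Conclusion.** The point holds, with medium confidence because of the unreadable material. The plan names UV on a photosensitizing drug as a possible cause of irreversible harm, controls it at entry, and leaves a later start to the investigator's judgment. The main-case figures (24 to 38 days at first UV, 36 to 87 days at the last fellow-eye lock-in) assume all visits are in window and eligibility is reconfirmed at primary-eye surgery. The 84- and 133-day figures are upper limits that apply only without that reconfirmation. The change should be made: the possible harm is serious, its frequency is unknown, and the remedy is cheap.

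**What to change.** Add one rule to 7.3.2.1. Systemic medications are checked before every light treatment, with a cross-reference if Table 1 or the Operator's manual already provides the check. If a drug covered by the photosensitizing or retinotoxic criteria of 6.2 has been started, UV is held and the Sponsor or medical monitor is contacted before proceeding, including on how to manage the unlocked lens. Section 7.3.2 already sends premature photopolymerization and aborted treatments to the Sponsor, so the route exists.

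The cost is one rule and at most one CRF question, at visits already scheduled. There are two downsides. Some treatments will fall outside their 3 to 7 day windows. The lens will also stay unlocked longer, and Section 9.12 warns that UV exposure before lock-in can change vision, so the rule should be hold-and-contact and not an open-ended stop. On the latest in-window schedule, a hold of more than 17 days passes the close of Month 3, so that subject's Month 3 accuracy and stability data would be pre-lock-in; on the shortest schedule the figure is 61 days. The Month 6 visit, which carries the primary effectiveness endpoints, keeps 107 to 151 days of room.
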